2.4 Sample Size Determination

The planned total sample size of 425 subjects (approximately 85 subjects per treatment group) provides at least 90% power to detect a 22% difference between ABBV-154 and placebo in ACR50 response rate at Week 12 (assuming a placebo ACR50 response rate of 13%), at a 2-sided significance level of 0.1 based on Chi-square test.

3.0 Endpoints

3.1 Primary Endpoint(s)

The primary endpoint is the achievement of ACR50 at Week 12.

3.2 Secondary Endpoint(s)

All secondary endpoints are at Week 12.

- Change in Disease Activity Score (DAS) 28 (CRP) from Baseline;

- Change in Clinical Disease Activity Index (CDAI) from Baseline;
- Achievement of ACR20;
- Achievement of ACR70;
- Achievement of low disease activity (LDA) defined by DAS28 (CRP) ≤ 3.2 ;
- Achievement of LDA defined by CDAI ≤ 10 ;
- Achievement of clinical remission (CR) defined by DAS28 (CRP) < 2.6 ;
- Achievement of CR defined by CDAI ≤ 2.8 ;
- Change in the Health Assessment Questionnaire Disability Index (HAQ-DI) from Baseline.

3.3 Other Efficacy Endpoint(s)

The primary endpoint and all secondary endpoints will be analyzed at all visits assessed other than Week 12. In addition, the following endpoints will be analyzed at all visits assessed.

- Change from Baseline in individual components of ACR
- Change from Baseline in simplified disease activity index (SDAI)
- Achievement of LDA defined as SDAI ≤ 11
- Achievement of CR defined as SDAI ≤ 3.3
- Achievement of Boolean remission based on a 28-joint count and defined as swollen joint count (SJC) ≤ 1 , tender joint count (TJC) ≤ 1 , high sensitivity C-reactive protein (hsCRP) ≤ 1 mg/dL, and Patient Global Assessment of Disease Activity ≤ 1 (on a 0-10 numeric rating scale [NRS])
- Change from Baseline in PROMIS Pain Interference
- Change from Baseline in FLARE-RA

3.4 Safety Endpoint(s)

Safety evaluations include adverse event (AE) monitoring, physical examinations, vital signs measurements, electrocardiograms (ECGs), and clinical laboratory testing (chemistry, hematology, and urinalysis).

Safety endpoints include the occurrence of the following:

1. Treatment-emergent adverse events, serious adverse events (SAEs), and AEs leading to discontinuation of the study drug
2. Potentially glucocorticoid related AEs
3. Potentially clinically important laboratory, vital signs, and electrocardiogram (ECG) parameters

3.5 Additional Endpoint(s)

Pharmacokinetic, immunogenicity, and biomarker research endpoints will be analyzed separately, and the corresponding analysis plan is not covered in this SAP.

4.0 Analysis Populations

The following population sets will be used for the analyses.

Intent-to-Treat (ITT) Population

The Intent-to-Treat (ITT) Population includes all randomized subjects who received at least one dose of study drug. The ITT Population will be used for all efficacy analyses. Subjects will be included in the analysis according to the treatment groups to which they are randomized.

Safety Population

The Safety Population in Placebo-Controlled Period (Safety_PC) includes all subjects randomized and received at least 1 dose of study drug in Placebo-Controlled Period. This population will be used for the safety analysis in the Placebo-Controlled Period.

The All ABBV-154 Treated Population (ALL_154) includes all subjects who receive at least 1 dose of ABBV-154 during the study. This population will be used to provide a comprehensive summary of safety.

For these safety populations (Safety_PC and ALL_154), subjects are assigned to treatment groups based on the treatments they receive during the majority of their drug exposure time in the analysis period for each subject in the respective safety population.

5.0 Subject Disposition

The total number of subjects who are screened, randomized, and treated will be summarized. Reasons for exclusion, including screen failure, will be summarized.

A summary of subject accountability will be provided where the number of subjects in each of the following categories will be summarized for each treatment group:

- Subjects randomized in the study;
- Subjects who take at least one dose of study drug;
- Subjects who complete protocol-specified treatment for Placebo-Controlled and LTE Periods 1 and 2, respectively;
- Subjects who prematurely discontinue study drug for Placebo-Controlled and LTE Periods 1 and 2, respectively;
- Subjects who complete study participation for Placebo-Controlled and LTE Periods, 1 and 2, respectively;
- Subjects who prematurely discontinue study participation for Placebo-Controlled and LTE Periods 1 and 2, respectively;
- Subjects in each analysis population, as applicable.

6.0 Study Drug Duration and Compliance

For the Placebo-Controlled period, LTE Period 1 and LTE Period 2, as well as study overall, duration of treatment will be summarized for each treatment group and for all ABBV-154 dose groups combined. Duration of treatment is defined for each subject as last dose date minus first dose date plus 14 days. Duration of treatment will be summarized using the number of subjects treated, mean, standard deviation, median, minimum and maximum. In addition, the number and percentage of subjects in each treatment duration interval (< 2 weeks [14 days], ≥ 2 weeks [14 days], ≥ 4 weeks [28 days], ≥ 8 weeks [56 days], ≥ 12 weeks [84 days], ≥ 24 weeks [168 days], ≥ 36 weeks [252 days], ≥ 52 weeks [364 days], ≥ 78 weeks [546 days], 104 weeks [728 days], 130 weeks [910 days], and 156 weeks [1,092 days]) will be summarized.

Treatment compliance will be summarized by treatment group and total ABBV-154 group for the safety populations. Treatment compliance is defined as the number of injections actually taken divided by the number of injections that should have been taken. All placebo injections will be included in the calculation for treatment compliance. Percent compliance will be summarized.

7.0 Demographics, Baseline Characteristics, Medical History, and Prior/Concomitant Medications

Demographics, baseline or disease characteristics, medical history, and prior and concomitant medications will be summarized for the ITT population overall and by treatment group. Categorical variables will be summarized with the number and percentage of subjects; percentages will be calculated based on the number of non-missing observations. Continuous variables will be summarized with descriptive statistics (number of non-missing observations, mean and standard deviation, median, minimum and maximum).

7.1 Demographics and Baseline Characteristics

Continuous demographic variables include age, weight, height, and body mass index (BMI). Categorical demographic variables include sex, ethnicity, race, age (< 40, 40 – 65, ≥ 65 years), weight (< 60, 60 – 100, ≥ 100 kg), BMI (< 25, ≥ 25 - < 30, ≥ 30 kg/m²), region (Asia, North America, or rest of world), tobacco user (current, former, never, unknown), and alcohol user (current, former, never, unknown).

Disease characteristics that will be summarized as continuous and categorical variables are listed below:

RA Medical History and Characteristics

- Duration of RA Symptoms in years
- Duration of RA Diagnosis in years
- Duration of RA Diagnosis Categories (< 5, 5 – 10 or ≥ 10 years)

ACR and/or DAS Components at Baseline

- Tender joint count (TJC28) defined as the number of tender joints out of 28 assessed joints used for DAS28 calculation
- Swollen joint count (SJC28) defined as the number of swollen joints out of 28 assessed joints used for DAS28 calculation
- Tender joint count (TJC68) defined as the number of tender joints out of 68 assessed joints used for ACR20/50/70 calculation
- Swollen joint count (SJC66) defined as the number of swollen joints out of 66 assessed joints used for ACR20/50/70 calculation
- Physician's global assessment of disease activity (on a 0-10 NRS)
- Patient's assessment of pain (on a 0-10 NRS)
- Patient's global assessment of disease activity (on a 0-10 NRS)
- Health Assessment Questionnaire Disability Index of the (HAQ – DI) (range: 0 to 3)
- High sensitivity C-reactive protein (hsCRP) (mg/L)

Other Baseline RA Disease Characteristics

- DAS28 (CRP)
- DAS28 Categories:
 - DAS28 > 5.1 (High Disease Activity)
 - DAS28 3.2 to \leq 5.1 (Moderate Disease Activity)
 - DAS28 < 3.2 (Low Disease Activity)
- Clinical Disease Activity Index (CDAI)
- CDAI categories:
 - CDAI > 22 (High Disease Activity)
 - CDAI >10 to \leq 22 (Moderate Disease Activity)
 - CDAI \leq 10 (Low Disease Activity)
- Simplified Disease Activity Index (SDAI)
- SDAI categories:
 - SDAI > 26 (High Disease Activity)
 - SDAI > 11 to \leq 26 (Moderate Disease Activity)
 - SDAI \leq 11 (Low Disease Activity)
- PROMIS Pain Interference Total Score and item level scores
- FLARE-RA (overall score, Joint and General subdomain scores, whether the subject experienced an RA flare in the last 3 months or since their last clinic visit [No/Yes, Once/Yes, several times], and whether the subject is currently flaring at baseline [No/Yes])
- Rheumatoid Factor (positive: \geq 10 IU/mL, negative: < 10 IU/mL)
- Anti-citrullinated protein antibody (ACPA) (positive, negative)

Prior and Concomitant Treatment Use

- Baseline glucocorticoid use (yes/no)
- Glucocorticoid dose at Baseline
- Prior failed Biologic and/or Targeted Synthetic DMARDs (1; 2 or more)
- Prior anti-TNF failure (yes/no)

- Prior anti-TNF use (yes/no)
- Prior adalimumab use (yes/no)
- Prior non-anti-TNF biologic DMARD use (yes/no)
- Prior synthetic (conventional and targeted) DMARD use (yes/no)
 - Prior conventional synthetic DMARD use (yes/no)
 - Prior targeted synthetic DMARD use (yes/no)
- Duration of prior glucocorticoid use (month)
- Duration of prior glucocorticoid-free days before randomization (day)
- Prior cumulative glucocorticoid dose (mg)
- Prior cumulative glucocorticoid dose (mg) (within one year before randomization)

7.2 Medical History

Medical history data will be coded using the Medical Dictionary for Regulatory Activities (MedDRA). The actual version of the MedDRA coding dictionary will be noted in the statistical tables and clinical study report. The number and percentage of subjects in each medical history category (by MedDRA system organ class and preferred term) will be summarized overall and by treatment group. The system organ class (SOC) will be presented in alphabetical order, and the preferred terms will be presented in alphabetical order within each SOC. Subjects reporting more than one condition/diagnosis will be counted only once in each row (SOC or preferred term).

7.3 Prior and Concomitant Medications

Prior and concomitant medications will be summarized by generic name. A prior medication is defined as any medication taken prior to the date of the first dose of study drug. A concomitant medication is defined as any medication that started prior to the date of the first dose of study drug and continued to be taken after the first dose of study drug or any medication that started on or after the date of the first dose of study drug, but not after the date of the last dose of study drug plus 70 days. The number and percentage of

subjects taking medications will be summarized by generic drug name based on the World Health Organization (WHO) Drug Dictionary for both prior and concomitant medications. The same summary will be provided specifically for DMARD medications, as well as for medications used for rescue therapy per protocol criterion.

8.0 Handling of Potential Intercurrent Events for the Primary and Key Secondary Endpoints

No intercurrent events are considered for the primary and key secondary endpoints.

9.0 Efficacy Analyses

9.1 General Considerations

All efficacy analyses will be conducted in the ITT Population. All tests will be 2-sided at an α level of 0.1.

The Primary Analysis will be performed after all ongoing subjects have completed the Placebo-Controlled Period, and the database has been locked. This will be the only and final analysis for the primary and secondary efficacy endpoints.

Unless otherwise specified, the categorical endpoints and continuous endpoints will be analyzed by Cochran-Mantel-Haenszel (CMH) and Mixed Model for Repeated Measures (MMRM), respectively, and the corresponding analyses are specified in Section 9.2.

Two of the baseline randomization stratification factors, prior anti-TNF failure and prior adalimumab use, will be combined into a single prior anti-TNF failure/adalimumab use factor (prior anti-TNF failure with adalimumab use; prior anti-TNF failure without adalimumab use; no prior anti-TNF failure) in the analysis methods. Other randomization stratification factors will be used without combination.

Unless otherwise specified, any subject who is randomized based on a wrong stratum will be analyzed according to the actual stratum the subject belongs to.

"Baseline" refers to the last non-missing observation before or on the day of the first administration of study drug or randomization if no study drug is given. Observations on the same day as the first administration of study drug will be considered for baseline, regardless of whether observation time (if available) was after the first administration of study drug time.

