5.7 Study Drug

ABBV-154 or placebo only will be manufactured and provided by AbbVie. It will be taken as SC injections in the abdomen or thigh beginning on Day 1 (Baseline). The study drug (ABBV-154 or placebo) will always be administered by a healthcare/ trained professional up to Week 78 (end of LTE Period 1). For LTE Period 2, study drug will be administered to all subjects by either site medical staff on-site or by the subject or designee (friend, family member, or personal health care professional), if opted for home dosing and where locally permitted. It should be taken at approximately the same time eow, preferably between 7 am and 11 am. A 15- to 30-minute post administration observation time is required. The study drug can be taken with or without food.

ABBV-154 and placebo syringes will be packaged in cartons with quantities sufficient to accommodate the study design. Each prefilled syringe and carton will be labeled per local requirements and these labels must remain affixed to the syringe and carton. Upon receipt, study drug should be stored as specified on the label (refrigerated at 2 to 8 degrees Celsius) and kept in a secure location. Each kit will contain a unique kit number. This kit number is assigned to a subject via Interactive response technology IRT and encodes the appropriate study drug to be dispensed at the subject's corresponding study visit. Study drug must not be dispensed without contacting the IRT system. Site staff will complete all blank spaces on the label before dispensing to subjects. Study drug is for investigational use only and will only be used for the conduct of this study.

AbbVie will provide instructions for drug preparation.

Table 2. Identity of Investigational Product

Study Drug	Dosage Form	Strength	Route of Administration	Manufacturer
ABBV-154	Solution for injection/infusion in pre-filled syringe	40 mg and 150 mg	subcutaneous	AbbVie
Placebo for ABBV-154	Solution for injection/infusion in pre-filled syringe	Not applicable	subcutaneous	AbbVie

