10.0 Safety Analyses

10.1 General Considerations

Safety data will be summarized for each safety population (Safety_PC and ALL_154). Safety summaries will be presented by treatment group, including a total group for all subjects on active study drug. For the safety analysis, subjects are assigned to a treatment group based on the treatment actually received, regardless of the treatment randomized.

"Baseline" refers to the last non-missing observation before or on the day of the first administration of study drug or randomization if no study drug is given. Observations on the same day as the first administration of study drug will be considered for baseline,

regardless if observation time (if available) was after the first administration of study drug time.

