10.2.1 Treatment-Emergent Adverse Events

Treatment-emergent AEs are defined as any AE with the onset that is after the first dose of study drug and with an onset date no more than 5 half-lives of the study drug (i.e., 70 days). Events where the onset date is the same as the study drug start date are assumed to be treatment-emergent, unless the study drug start time and the AE start time are collected and the AE start time is prior to the study drug start time. All treatment-emergent AEs will be summarized overall, as well as by primary MedDRA SOC and Preferred Term. The SOCs will be presented in alphabetical order, and the PTs will be presented in alphabetical order within each SOC.

The number and percentage of subjects experiencing treatment-emergent AEs will be summarized.

In the ALL_154 population, treatment-emergent AEs are defined based on the first dose of ABBV-154.

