10.4 Analysis of Vital Signs

Vital sign measurements of systolic and diastolic blood pressure, respiratory rate, pulse rate, and body temperature will be summarized. Weight will be included in the summaries.

Each vital sign variable will be summarized for all time points (starting with Baseline) with the number of non-missing observations, mean and standard deviation, median, minimum and maximum. Mean change from baseline to each applicable post-baseline visit will be summarized for each vital sign variable, with the number of observations, baseline mean, and visit mean. The change from baseline mean, standard error, and 95% confidence interval will be presented for the mean change from baseline within each treatment group and difference between treatment groups (ABBV-154 vs. placebo) as applicable. This summary and change from baseline summary will be presented once by treatment sequence.

Vital sign variables will be evaluated based on PCI criteria. Pulse rate, body temperature, and respiratory rate will follow the criteria in Appendix B. All other vital signs will follow the criteria in the PSSAP. For each vital sign PCI criterion, the number and percentage of subjects who have a vital sign value meeting the criteria will be summarized. Listings will be provided to summarize subject-level vital sign data for subjects meeting PCI criteria. In the evaluation of PCI vital sign values for the ALL_154 population, the baseline value will be determined by the last non-missing measurement recorded on or before the date of the first dose of study drug in the corresponding ABBV-154 treatment group.

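### The safety baseline rule lets a timed post-dose reading on the day of first dose replace that day's pre-dose value

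*SAP*

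**What the plan says.** SAP 10.1 governs the safety summaries. Baseline is the latest available value up to the day of first dose, and a same-day value qualifies "regardless if observation time (if available) was after the first administration of study drug time".

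SAP 9.1 gives the same rule for efficacy: baseline "refers to the last non-missing observation before or on the day of the first administration of study drug". Clock time is set aside there too, and a Day 1 reading is admitted on the same terms, "regardless of whether observation time (if available) was after the first administration of study drug time".

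SAP 10.4 sets the baseline for PCI vital signs in ALL_154 as the "last non-missing measurement recorded on or before the date of the first dose of study drug in the corresponding ABBV-154 treatment group". SAP 10.3 uses the same date-only construction for PCI laboratory values. For subjects randomised to placebo, the date in question is that of their first ABBV-154 dose at Week 12.

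Two provisions limit the effect:
- SAP 10.3 excludes SAE-related laboratory tests from baseline. It does not say whether the cut-off for this exclusion is judged by date or by time, and SAP 10.4 has no such exclusion for vital signs.
- SAP 10.2.1 counts an AE starting on the day of first dose as emerging on treatment, with one exception: "unless the study drug start time and the AE start time are collected and the AE start time is prior to the study drug start".

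Protocol 5.7 adds that "A 15- to 30-minute post administration observation time is required".

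**The concern.** Because the rule takes the latest same-day value, it does more than tolerate a post-dose reading. It prefers that reading to an earlier pre-dose one, even when recorded times show the order. A second reading on the dosing day is most plausible in a subject who is unwell after the injection, since subjects are observed after dosing and monitored for hypersensitivity (Protocol 6.2).

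Two things then go wrong for that subject. The abnormal reading is no longer a post-baseline value, so it drops out of the change, shift and PCI summaries. It also becomes the reference for every later visit. PCI laboratory and vital sign values are a listed safety endpoint (SAP 3.4). If such reactions are drug-related, the loss falls mainly on the active arms of Safety_PC and pulls the comparison with placebo towards no difference.

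**Working it through.** The plan gives no figure that depends on this rule, and the sample size calculation is not affected. The check applies the written rules to assumed readings.

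**Inputs**
- High pulse PCI rule (SAP Table B2): value ≥ 120 bpm and increase ≥ 15 bpm from baseline.
- Low pulse PCI rule (same table): value ≤ 50 bpm and decrease ≥ 15 bpm.
- SAP 10.4 counts subjects meeting a criterion, not readings.
- About 85 subjects per group (SAP 2.4).
- Pulse and pain values below are assumptions; none come from the documents.

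**1. High pulse: 80 before and 125 after the first injection, same day**

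| | Rule as written | Last pre-dose value |
|---|---|---|
| Baseline | 125 | 80 |
| Day 1 reading of 125 | is the baseline, so not flagged | 125 − 80 = +45, flagged |
| Lowest later pulse flagged high | max(120, 125 + 15) = 140 | max(120, 80 + 15) = 120 |
| Change at a later pulse of 80 | 80 − 125 = −45 | 80 − 80 = 0 |

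The PCI count differs by one subject (0 against 1) unless a later pulse reaches 140. One subject in 85 is 1/85 = 1.2% of a group. The spurious change of −45 moves a group mean by 45/85 = 0.5 bpm.

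**2. Low pulse: 55 before, 70 after, 50 at a later visit**
- As written: 70 − 50 = 20, flagged.
- Pre-dose baseline: 55 − 50 = 5, not flagged.

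The rule can therefore create a flag as well as remove one.

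**3. Reach within the criteria**
- Of the vital signs in Table B2, only pulse is defined relative to baseline.
- Temperature and respiratory rate have absolute limits, so a later abnormal value is still caught. Only the Day 1 reading is at risk, if PCI is judged on post-baseline values.
- The remaining vital signs follow the PSSAP, which is not among the documents.
- The liver thresholds in SAP 10.3 are absolute.

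**4. Reach within the populations**
- Safety_PC contains active and placebo arms, so dilution is possible there.
- ALL_154 contains only ABBV-154-treated subjects. A wrong baseline there affects individual flags but no placebo comparison.

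**5. Efficacy (SAP 9.1)**

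With Week 12 pain of 3, improvement is (6 − 3)/6 = 50% from a baseline of 6, (5 − 3)/5 = 40% from 5, and (7 − 3)/7 = 57% from 7. A changed Day 1 value can move an ACR50 component across the 50% line either way. The documents give no reason to expect a direction.

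**6. Other analyses that might cover it**

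The only alternative baseline (SAP 9.3.3) widens the window to 7 days after first dose for four ACR components. No planned analysis uses a strictly pre-dose baseline.

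**The case against.** The strongest reply is that little is lost and the situation may be rare. Several parts of it stand.

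- **The reaction is still reported.** A reader might infer that a first-dose reaction vanishes from the safety data. It does not: SAP 10.2.1 counts a same-day AE as treatment-emergent, and hypersensitivity and serious allergic reactions are safety topics of interest (Protocol 6.1). Only the numeric reading drops out.
- **The AE rule is not a contradiction.** A reader might see SAP 10.2.1, which uses clock time, as conflicting with SAP 10.1, which ignores it. The AE rule uses time only to remove events shown to start before dosing. It is an inclusive rule for another kind of data.
- **Frequency is unsupported.** Protocol 5.7 requires observation, not repeat measurement. The Activity Schedule shows a single Baseline entry for vital signs, hematology and chemistry. The reaction sample in Protocol 6.2 is for tests listed in the Operations Manual, not stated to be routine safety laboratory tests. That manual, not supplied, may also fix the order of Day 1 procedures.
- **A strict pre-dose rule could harm efficacy.** Joint counts and hsCRP are also taken at Screening, up to 35 days earlier. Pain, both global assessments and HAQ-DI are not. Barring every post-dose Day 1 value could send some ACR components back to Screening while others stay on Day 1.

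None of this answers the case where both a pre-dose and a post-dose value exist on the dosing day with recorded times. A fixed procedure order would not prevent an unscheduled repeat after a reaction, and in that case the written rule selects the wrong value.

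**Conclusion.** The point holds, narrowly. For a subject with timed pre-dose and post-dose vital signs or non-SAE laboratory values on the day of first dose, SAP 10.1 takes the wrong one as baseline. The PCI baselines in SAP 10.3 and 10.4 do the same on the day of first ABBV-154 dose. In the pulse example this costs one flagged subject and raises the later high-pulse threshold from 120 to 140.

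The number of subjects affected cannot be derived from the documents and is probably small, because no post-dose set of vital signs or safety laboratory tests is scheduled on Day 1. Purely as an assumption, 1% to 3% of 425 would be about 4 to 13 subjects; nothing in the plan supports that range.

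A reader might infer that the whole active-placebo safety comparison, or the ACR50 result, is biased. The documents do not support either. Dilution applies to Safety_PC only, and depends on reactions being drug-related and on readings being repeated in those who react. The effect on ACR50 has no known direction and is probably small.

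**What to change.** In SAP 10.1, 10.3 and 10.4, add the following. Where recorded times show both a pre-dose and a post-dose value on the day of first dose (first ABBV-154 dose for ALL_154), baseline is the last pre-dose value of that day, and the timed post-dose value counts as post-baseline.

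Keep the current rule in two cases: when times are missing, and when the only same-day value is post-dose. In the second case the value serves as baseline only and is not also counted as post-baseline. No subject then loses a baseline.

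In SAP 9.1 go no further than this same-day preference, so that no ACR component reverts to a Screening value. In SAP 10.3, state whether the SAE-related exclusion works by date or by clock time.

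The cost is a few lines of SAP text and a small change to one derivation. No new data are collected, and sample size and power are unchanged. The change helps only where times were recorded; the SAP says no more than that they may be available.
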